## **List of Common Abbreviations in Protocol:**

• BH: Behavioral health

• IBD: Inflammatory bowel disease

• SMH: Specialty medical home

• UPMC ISD: UPMC Insurance Services Division

## **Research Synopsis**

**Study Population:** This research study will examine the impact of two existing approaches for delivering care within a specialty medical home (SMH) clinical model for patients with inflammatory bowel disease (IBD) and behavioral health (BH) conditions. Care approaches available to patients include traditional high-touch care delivered by a multidisciplinary team of IBD and BH clinicians (TEAM) and a health technology-based (TECH) approach that uses telemedicine and other evidence-based digital tools designed to deliver accessible, convenient care. This study seeks to understand the differential impact of TEAM and TECH on important health outcomes such as IBD and BH symptom severity, functional impairment, health care service utilization and costs, patient quality of life, and patient disease self-management.

**Study Design:** A comparative effectiveness study using an individual-level randomized design along with a pragmatic, mixed-methods approach to compare two evidence -based SMH care strategies (e.g. high-touch multidisciplinary care and low-human touch technology-enhanced care). Quantitative (e.g. self-report, electronic health record, process) and qualitative (e.g. interviews) data will be collected across multiple time points during the study period.

**Sample Size:** We expect to enroll 675 individuals.

**Study Duration:** The contract period begins February 1, 2019 and concludes September 30, 2026. Participants were actively enrolled in the study between July 1, 2019 and February 28, 2024.

**Primary Aim 1:** Examine the impact of TEAM vs. TECH on two main patient-centered outcomes of IBD and BH symptom severity and secondary outcomes of functional impairment, healthcare utilization, quality of life, and self-efficacy.

**Hypothesis 1:** Both TEAM and TECH approaches will result in clinically meaningful improvement across all outcomes.

**Primary Aim 2:** Examine the impact of patient characteristics on clinical response to TEAM or TECH approaches and establish subgroups of patients who will benefit most from each approach. The study focused on baseline IBD activity and age as primary moderators but secondarily explored site, IBD diagnosis, and health literacy.

**Hypothesis 2a:** The TEAM approach will show greater effects in those with active IBD, while TECH will show greater effects in those with inactive IBD.

**Hypothesis 2b:** The TECH approach will improve outcomes more in younger patients.

**Primary Aim 3:** Examine IBD patient and provider perspectives on facilitators and barriers to efficient and effective implementation of TEAM and TECH and the potential for scaling the interventions and SMH model to other common chronic diseases and community care settings to inform high-quality, efficient ongoing implementation and dissemination.

## **Background and Significance**

Inflammatory bowel diseases, including Crohn's disease (CD) and ulcerative colitis (UC), are among the most costly gastrointestinal (GI) conditions in the United States (US) and are lifelong chronic diseases that, if not well managed, can significantly disrupt the lives of individuals. IBD afflicts three million U.S. patients and families with incidence rising globally, especially among younger age groups, during a critical social and career development period. IBD is a relapsing and remitting condition associated with varying degrees of GI inflammation (disease activity) and related symptoms of abdominal pain, diarrhea, nutritional deficits and fatigue. In the presence of anxiety and depression, IBD symptom load is even higher, even when inflammation is mild or absent. IBD carries a financial burden between \$14-31 billion annually in the U.S., with about 30% of adult IBD patients accounting for more than 80% of IBD-related healthcare spend; the largest drivers of cost are surgeries and hospitalizations, many of which are preventable. Prior studies have shown that medical utilization (both emergency department (ED) visits and unplanned hospitalizations) is driven by serious disease and IBD activity requiring steroids, biologics, or surgery, chronic unexplained pain and related opioid use, and unaddressed or undertreated behavioral health (BH) problems.

IBD patients exhibit higher rates of comorbid BH conditions, especially anxiety and depression, than healthy counterparts – these further compound disease complexity. Indeed, when present, BH issues directly and negatively impact medical/surgical treatment response, adherence to treatment regimens, care utilization including surgeries, and disease-related quality of life and functioning. Emerging adults with IBD are a large and uniquely vulnerable subpopulation who, if not effectively integrated into an adult-centered healthcare system, are at significantly higher risk for poor disease outcomes, Including high rates of anxiety and depression. Beginning in 2020, BH symptoms were further exacerbated by the COVID-19 pandemic, particularly for IBD patients who reported elevated levels of anxiety surrounding their vulnerability and concerns about securing needed care.

Unfortunately, BH care has been siloed, falling short of the seamless, integrated health care necessary for complex patient populations. Most existing models of chronic, lifelong disease management do not adequately address psychosocial issues, nor necessarily address the individualized, whole health needs of patients at different stages of their lives, despite the recognized importance of these issues and their impact on health outcomes. Healthcare systems have not found optimal ways to provide integrated behavioral support in routine care, leading to unidentified or undermanaged psychological issues, impaired disease self-management, and poor healthcare access and coordination. Page 27-33

In recent years, there has been transformative and widely accepted change around how care is organized and delivered with emphasis on meeting patients where they are. In primary care, medical home models have growing evidence for clinical efficacy, improved care quality,

and reduction in medical utilization and costs.  Published studies show that these results are also attainable in specialty medical homes (SMH) including those focused on IBD.  Despite proven success, such intensive, highly staffed and resourced models are expensive to implement and may not be necessary for all chronically ill patients.  Workforce limitations and patient concerns related to time, distance, and cost suggest that on-site multidisciplinary teams alone may not be sufficient to provide effective and efficient patient-centered care for the growing number of individuals with chronic diseases like IBD. Health technology, including digital interventions, remote monitoring of health outcomes, and telemedicine visits, is one way to address this gap with growing evidence linking its use to improved access and adherence to BH care and better outcomes.  Patient preference results already support team-based care and health technology within SMHs,  but less is known about how these models impact the outcomes that patients care about most and how to efficiently and effectively implement, maintain, and disseminate these approaches.

## **Objectives**

The goal of this collaborative study is to provide evidence on the impact of two-evidence based SMH approaches on patient-centered disease and healthcare utilization outcomes at three academic medical centers in the northeastern US – UPMC in Pittsburgh, PA, Mount Sinai Hospital (MSH) in New York, NY, and the Cleveland Clinic Foundation (CCF) in Cleveland OH.

To ensure our study's focus was patient-centered, the study team worked closely with patient-, provider-, and system-level stakeholders to develop all aspects of this study protocol, including the early development efforts of in-person and technology-supported care approaches, the research questions, the study outcomes, the evaluation procedures, and the dissemination strategies included in this protocol.

## **Aims**

This study aimed to compare the effectiveness of two evidence-based, patient-centered behavioral approaches implemented within three existing medical homes: **TEAM**, a high-human touch multidisciplinary team-based approach delivered at point-of-care, and **TECH**, a low-human touch technology-based approach delivered at the patient's convenience with the guidance of health coaches. The study focused on patient-centered outcomes, impact on healthcare utilization, determining which intervention worked best for whom, and potential scalability of the model to other healthcare environments and for other chronic conditions.

**Primary Aim 1:** Examine the impact of TEAM vs. TECH on two main patient-centered outcomes of IBD and BH symptom severity and secondary outcomes of functional impairment, healthcare utilization, quality of life, and self-efficacy.

**Hypothesis 1:** Both TEAM and TECH approaches will result in clinically meaningful improvement across all outcomes.

**Primary Aim 2:** Examine the impact of patient characteristics on clinical response to TEAM or TECH approaches and establish subgroups of patients who will benefit most from each approach. The study focused on baseline IBD activity and age as primary moderators but secondarily explored site, IBD diagnosis, and health literacy.

**Hypothesis 2a:** The TEAM approach will show greater effects in those with active IBD, while TECH will show greater effects in those with inactive IBD.

**Hypothesis 2b:** The TECH approach will improve outcomes more in younger patients.

**Primary Aim 3:** Examine IBD patient and provider perspectives on facilitators and barriers to efficient and effective implementation of TEAM and TECH and the potential for scaling the interventions and SMH model to other common chronic diseases and community care settings to inform high-quality, efficient ongoing implementation and dissemination

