## Study Design/Methodology

This multi-center study will involve an individual-level randomized design along with a pragmatic, mixed-methods approach to compare two existing care approaches, TEAM (high-human touch) and TECH (technology-supported care), for delivering IBD and behavioral health services to individuals with IBD within and SMH model. Participants will be actively enrolled in the study for 12 months. Study participants will receive care from the IBD SMH clinical team per usual care delivery processes established for TEAM and TECH for the duration of the study.

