#### **Secondary outcomes**

Functional impairment will be measured using the Short Form 12 Health Survey Version 2 (SF-12v2) which includes 12 items from the Short-Form 36 Health Survey and yields a physical and mental composite score as well as 8 subscale values: physical functioning, role-physical, bodily pain, general health, vitality, social functioning, role-emotional, and mental health. Lower scores correspond with poorer health-related functioning/quality of life.

IBD-IBS Symptom Severity. The Irritable Bowel Syndrome Symptoms Severity Scale (IBS-SSS) more accurately captures IBD symptom severity for many individuals with IBD, particularly those with inactive IBD but persistent functional GI symptoms (e.g., IBD-IBS). The IBS-SSS scores pain severity, pain frequency, abdominal bloating, bowel satisfaction and interference with life on a 0-100 scale with a total score of 500. A 50-point or more reduction in this score is considered clinically meaningful.

Health care utilization will be captured categorically via medical record data including ED visits and hospitalizations.

Patient engagement will be measured using the IBD Self-efficacy Scale which assesses one's confidence level in managing stress and emotions, managing medical care, managing symptoms and disease, and maintaining remission.

Quality of life will be measured using the Short Quality of Life in Inflammatory Bowel Disease Questionnaire (SIBDQ) $^{71}$ .

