## **Statistical Analysis Plan**

## **Sample Size and Power Calculations**

The bundles of TEAM and TECH services have been tested as packages. For the TEAM approach, we evaluated the feasibility, durability, and impact of the IBD specialty medical home for 346 IBD patients after one year of enrollment. In the year following enrollment, there was a significant reduction in IBD disease activity for both UC (p=.0003) and CD (p=.002), unplanned care (both ER visits (p<.0001) and hospitalizations (p=.008), while there was an observed improvement in health-related quality of life (p<.0001), depression (p<.0001) and anxiety (p=.02). For the TECH approach, a combination of digital tools- an app based cognitive behavioral program, remote monitoring and telepsychiatry (TECH) was compared to behavioral treatment as usual (control) using a randomized trial prospective design for patients with IBD with anxiety and/or depression. There was a significantly greater reduction in anxiety in the TECH group over 3 months (delta 5.6); CI (3.9, 7.6); p<.0001; n=34) than in the control group (delta 2.5; CI (0.5, 4.6); p=.02; n=35. There was also a greater reduction in depression (delta 2.6 CI (0.6, 4.6); p=.01 in the active versus control group (delta=.0.4; CI (-2.2, 3.1); NS). 76 Ninety-six percent of patients in TECH group engaged with the digital CBT program and participated in remote monitoring with 69% completing a clinically meaningful number of sessions. Both studies were conducted in "real world" clinical setting and powerfully show how both approaches can provide powerful solutions in improving health care delivery in sustainable ways.

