#### **Quantitative Analysis**

We will conduct descriptive analyses and multivariate modeling of data to examine changes in outcomes over time and explore moderating variables. All analyses will be intent to treat and conducted as described in our analytic plan and associated protocol. If diagnostic or sensitivity analyses dictate changes to those plans, we will clearly identify subsequent analyses as ad hoc or otherwise deviating from an a priori plan, including labeling subgroup and interaction analyses as confirmatory, exploratory, or post hoc. Our statistician will remain masked to study arm to reduce bias.

Prior to hypothesis testing for Aims 1 and 2, data will be explored by descriptive data analysis. Summary statistics including means, standard deviations, medians, and ranges for continuous variables, or frequencies and percentages for categorical variables, will be presented for the entire sample and stratified by approach at each time point. We will assess the balance of key covariates by visually assessing the standardized differences. We will conduct baseline data analysis for each outcome to explore any pre-intervention differences in outcomes between TEAM and TECH at baseline. Two-sided Wald T-test or Wald F-test using the generalized linear mixed models (GLMMs) with normally distributed random effects for three sites will be used. This estimating method using GLMMs will produce consistent estimations of the regression parameters under the missing at random (MAR) or missing completely at random (MCAR) mechanism. The MAR assumption will be verified in the sensitivity analysis (see handling missing data in quantitative analyses). Distributions of outcomes and key covariates over time will also be visually examined to identify systematic departures from normality and overall pattern over time, assisting us in evaluating the distribution of data and determining if assumptions are met for subsequent modeling approaches. We will conduct statistical analysis on transformed outcomes using Box Cox- or log-transformation to address any asymmetry.

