Aim 1 will examine the impact of TEAM vs. TECH on the primary and secondary outcomes and will determine if changes in outcomes over time are different between the two groups. We will fit the GLMMs to associate each outcome with the intervention (TEAM vs. TECH) and other covariates of interest. To account for the within-patient correlation in longitudinal data and to reflect potential differences among three sites, we will add normally distributed random effects for patients and sites in addition to the fixed effects for intervention and covariates of interest. An inference of the intervention effects for each outcome will be carried out using Wald test based on the either F-distribution or Chi-square distribution as appropriate. For each outcome, the null hypothesis of homogeneous change in outcomes overtime between TEAM and TECH will be examined by testing the treatment-by-time interaction effect on each outcome. In the absence of significant interaction effects, the marginal difference in outcomes between TEAM and TECH will be examined using the same GLMMs without the interaction effect. All hypothesis tests for Aim 1 will be conducted at the overall significance level of 0.05. The score changes from baseline to each time point and their difference between TEAM and TECH will be estimated with 95% confidence intervals.

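### Hypothesis 1 says each approach causes improvement, but Aim 1 tests only TEAM against TECH; within-arm change can describe improvement, not attribute it to either approach

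*Combined protocol and SAP*

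**What the plan says.** All references are to the combined protocol and SAP.

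- **Hypothesis** (Research Synopsis and Aims): "Both TEAM and TECH approaches will result in clinically meaningful improvement across all outcomes". Aim 1, in the sentence above it, is already worded as TEAM versus TECH.
- **Arms** (Study Design/Methodology): the trial will "compare two existing care approaches, TEAM (high-human touch) and TECH (technology-supported care"). No untreated or usual-care arm is described.
- **Test** (Quantitative Analysis, Aim 1): "the null hypothesis of homogeneous change in outcomes overtime between TEAM and TECH will be examined by testing the treatment-by-time interaction effect". If the interaction is not significant, the overall difference between the arms is tested in the same model without it.
- **Estimates** (same paragraph): "The score changes from baseline to each time point and their difference between TEAM and TECH will be estimated with 95% confidence intervals". No within-arm test or success criterion is attached.
- **Threshold** (Secondary outcomes, IBS-SSS): "A 50-point or more reduction in this score is considered clinically meaningful". Neither primary outcome has a corresponding value.
- **Pilot** (Sample Size and Power Calculations): in a randomized comparison with behavioral treatment as usual, the 3-month anxiety reduction was greater with TECH (5.6 points, n=34) "than in the control group (delta 2.5; CI (0.5, 4.6); p=.02; n=35").

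**The concern.** The stated primary hypothesis and the planned primary test address different questions. The hypothesis concerns what each approach does compared with not receiving it. The test concerns whether the two approaches differ. Only the change from baseline within each arm bears on the hypothesis, and that change has no control.

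What is at stake is the trial's main conclusion. If both arms improve, the wording of Hypothesis 1 invites the statement that both approaches worked. Randomization protects the TEAM-TECH contrast, because influences common to both arms cancel. It gives no protection to the change within an arm.

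**Working it through.** **1. Can the planned test separate Hypothesis 1 true from false?**

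| True state | Hypothesis 1 | Expected TEAM-TECH difference |
|---|---|---|
| Both approaches cause equal, sufficient improvement | true | none |
| Neither has an effect; both arms drift equally | false | none |
| Both cause sufficient improvement, one more than the other | true | present |
| Only one causes improvement | false | present |

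A null result and a positive result each occur under both states of the hypothesis. This holds for the interaction test and for the overall difference that follows it.

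**2. Can the within-arm changes fill the gap?** They can show that scores fell. Three facts in the documents stop them from showing why.

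- Inclusion Criteria: entry requires PHQ-4 of at least 6. The behavioral outcome, PHQ-ADS, is a different score but measures the same symptoms, so some fall by regression to the mean is expected. Patients are not selected on IBD activity (active and inactive are both enrolled and stratified), so this argument does not carry over to the IBD outcome.
- Background and Significance: IBD relapses and remits. Change can therefore occur without treatment, although the documents do not show in which direction the average would move.
- Sample Size and Power Calculations: the pilot control group improved on anxiety.

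**3. What the pilot shows.** Share = control change / TECH change; contrast = TECH change − control change.

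| Outcome | TECH | Control | Share | Contrast |
|---|---|---|---|---|
| Anxiety | 5.6 | 2.5 (CI 0.5 to 4.6, p=.02) | 2.5/5.6 = 0.446 | 3.1 |
| Depression | 2.6 | about 0.4 (CI −2.2 to 3.1, NS) | 0.4/2.6 = 0.154 | 2.2 |

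The control value for depression is printed with a stray decimal point. The interval's midpoint, (−2.2 + 3.1)/2 = 0.45, supports reading it as 0.4. For anxiety, a pre-post reading would credit TECH with 5.6 points where the controlled contrast is 3.1. For depression the gap is small, and the control change is not distinguishable from zero.

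**4. Illustration with an assumed drift.** Suppose neither approach has any effect and both arms drift down by δ, in SDs of the change score. The documents give no δ, so 0.1 to 0.3 is an assumption. With the plan's 252 per arm after attrition, the one-sample noncentrality is δ√252. Squaring the single-arm probability (arms taken as independent) gives the chance that both 95% intervals exclude zero on the side of improvement.

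| δ | δ√252 | One arm | Both arms |
|---|---|---|---|
| 0.1 | 1.59 | 0.3525 | 0.12 |
| 0.2 | 3.17 | 0.8855 | 0.78 |
| 0.3 | 4.76 | 0.9973 | 0.99 |

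At this sample size, intervals that exclude zero in both arms are weak evidence that either approach worked.

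**The case against.** **Hypothesis 1 can be assessed.** A descriptive reading, that mean change in each arm reaches a stated size, can be judged from the planned intervals once a threshold exists. This stands. A reader might infer that Hypothesis 1 is untestable in every sense, but only its causal wording is out of reach.

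**The harm is not documented.** A reader might infer that the plan commits to reporting pre-post change as confirmation. No section says so. The only planned Aim 1 inference is between randomized arms. For the case where the arms do not differ, the plan says only that the results can suggest TECH is feasible and frees TEAM to be used more efficiently. This stands: the risk lies in the wording.

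**The anxiety figure is selective.** It must be read with depression, where the share is about 15% and not significant. The control was also a treated comparator with n=35, so its 2.5-point fall does not isolate regression to the mean or time trends. Both points stand. The pilot shows that improvement can occur without TECH; it does not measure the artefact to expect here.

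**The pandemic is already handled.** The plan adjusts for COVID-confounded status (211 of 675) and repeats the analysis in the 432 later enrollees. The Background says the pandemic worsened behavioral symptoms, so it does not clearly favour spurious improvement. It is not counted here.

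**The power statement.** A reader might infer from the claim of over 99.9% power that Aim 1 was really planned as a within-arm test. The plan ties no effect size to that figure, so its origin cannot be established, and this point does not rely on it.

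**Conclusion.** The concern holds in a limited form. As worded, Hypothesis 1 can be neither supported nor refuted by the only test planned for Aim 1, and the planned within-arm estimates can describe improvement but not attribute it. This rests on the documents' own wording and on the absence of an untreated or usual-care arm. It does not depend on the assumed drift.

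The size of any misattribution in this trial is unknown. The pilot gives one controlled comparison per outcome, with control shares of 45% (anxiety) and about 15% (depression, not significant), both imprecise. A general regression-to-the-mean figure is tempting, but the documents give neither the entry distribution nor a test-retest correlation, and such a figure would not apply to the IBD outcome.

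Two active arms are a legitimate comparative-effectiveness design, and no control arm is called for. The missing threshold for the primary outcomes is missing detail rather than a separate error; it matters only if the language of clinical meaning is kept.

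**What to change.** - In the Research Synopsis and Aims, restate Hypothesis 1 as the TEAM-versus-TECH contrast that the Aim 1 analysis tests.
- In the Aim 1 paragraph of Quantitative Analysis, keep the within-arm changes and their intervals, label them descriptive, and state that they will not be taken as evidence that either approach caused improvement.
- Record this as a dated amendment. Enrolment closed in February 2024, and Quantitative Analysis already commits to identifying departures from the prior plan.
- If the language of clinical meaning stays, name a threshold for each primary outcome before unblinding and use it to interpret the continuous estimates. A responder analysis is optional: it dichotomizes continuous scores and adds tests.

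The cost is a few sentences and a less favourable claim, with no new data and no required new analysis. One limit remains: without an equivalence or non-inferiority margin, a non-significant contrast will not show that the approaches are alike, and the interval for the difference should be reported in that light.
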